## **Non-hematological Exemptions:**

The following events are expected due to IMP and administration route and, if self-limiting and resolved within a short timeframe, will not constitute DLTs but should be reported as AEs/SAEs according to reporting guidelines:

- Grade 3 laboratory values considered not clinically significant
- Grade 3 fever without neutropenia (lasting less than 5 days)
- Grade 3 headache or vomiting for less than 48 hours (with adequate supportive care).
- Grade 3 nausea and fatigue, persisting for less than 7 days (with adequate supportive care).

### **3.1.2. Maximum Tolerated Dose and Recommended Phase II Dose Definition**

The MTD is identified as the highest non-toxic dose level on which 6 patients have been treated, i.e., the dose level immediately below that at which 2 or more DLTs were observed and dose escalation was stopped. If only 3 patients were treated at the immediately lower dose level, 3 additional patients will be recruited at this dose level to ensure that no more than 1 DLT occurs out of 6 patients.

The RP2D will be defined as the highest tolerable dose, MTD, or a lower dose. For example, the RP2D may be lower than the MTD if accumulated toxicity over 2 cycles at the MTD is judged or proved to be non-tolerable.

### **3.1.3. Part 2 (Cohort-expansion Phase)**

Part 2 will be conducted in approximately 24 patients with medulloblastoma recurrent or refractory to frontline therapy and, if they have recurrent disease, they must have received second-line chemotherapy for progressive disease (PD). Patients with a maximum of 1 recurrence of disease will be included.

Patients will receive Lu-DTPA-omburtamab at the RP2D determined in Part 1.

Lu-DTPA-omburtamab will be administered via an indwelling intracerebroventricular access device (e.g., Ommaya catheter) on Day 1 of each treatment cycle. Patients who are not discontinued from treatment (according to the criteria in [Section 4.3.2](#)) will be eligible for another treatment cycle at the same dose administered in the first cycle, up to a maximum of 5 treatment cycles per patient. The expected cumulated absorbed dose calculated based on the dosimetry data in the escalation part will assist in guiding (by the DMC) the maximum number of cycles feasible in the expansion phase.

Patients can be treated in an outpatient setting or can be admitted as inpatients for infusions; however, all patients should be observed for a minimum of 2 hours after end of each infusion.

Patients will undergo monitoring for AEs; routine safety assessments (vital signs, clinical chemistry, hematology); CSF sampling for total protein, glucose, ctDNA (if the patient has given informed consent to this analysis), and cell count; blood and CSF draws for PK; and blood and CSF draws for potential culture (only in case of elevated body temperature); neurological assessments and radiographical investigation for evaluation of neurological AEs; assessment of performance status (Lansky [ $<16$  years] or Karnofsky [ $\geq 16$  years] scales). CSF and blood will be drawn for PK and ADA analysis. Efficacy assessments include brain and spine MRI, CSF cytology, and neurological examination.

Patients will return for an EOT Visit 5 to 6 weeks after the last dose and for regular Follow-up Visits up to 104 weeks after the last infusion of Lu-DTPA-omburtamab to assess safety, efficacy, secondary malignancies, and long-term survival. In addition, all patients who are dosed with Lu-DTPA-omburtamab will be regularly monitored for secondary malignancies (see [Section 7.4.5.3](#)) for at least 10 years after end of trial, or until death, if sooner. This post-trial monitoring can be conducted by contacting the patient or the general practitioner, the referral site (if applicable), or by checking medical records or other sources.

### 3.2. Discussion of Trial Design

The sequential-group, escalating-dose design of Part 1 will ensure that safety and tolerability are assessed at lower dose levels before progressing to dosing at higher doses. The 3+3 dose-escalation algorithm employed will prevent unnecessary exposure to the trial drug by allowing dose-escalation decisions to be made based on smaller, 3-patient dose levels in the absence of DLTs, while enabling a dose level to be expanded to 6 patients where necessary to provide more information on the incidence of DLTs. The first enrolled patient at each dose level will be observed for a minimum of two weeks after the treatment dose before subsequent patients will be dosed

As there is relevant and substantial clinical experience from the comparable drug I-omburtamab (see [Section 1.1](#) and [Section 1.2.1](#)), this enrolment strategy is considered appropriate for this trial.

Patients will be closely monitored for safety and efficacy throughout the treatment periods and up to 6 weeks (Part 1) and 104 weeks (Part 2) after the last dose. Considering the baseline advanced disease, and that most if not all patients have received high-dose cranial spinal irradiation prior to trial inclusion, 104 weeks in Part 2 appears to be a relevant follow-up duration in these advanced cancer patients with limited survival. A DMC will monitor safety data during Part 1 and make recommendations on dose escalation. All patients will be additionally monitored for secondary malignancies throughout the trial and for at least 10 years after end of trial, or until death, if sooner.

The trial will be conducted in 2 parts. The dose-escalation phase (Part 1) of the trial will be conducted prior to starting the cohort-expansion phase (Part 2) so that the safety data from Part 1 may inform the RP2D for Part 2.

For the first treatment dose level at 10 mCi, a single patient will be dosed at an anticipated low first-in-human starting dose level. Given the myelosuppression observed after IV injection in our

mouse studies, a 10 mCi starting dose level is proposed which corresponds to an 8-fold safety margin over the highest no-adverse-events dose administered IV in the mice (200  $\mu$ Ci corresponds to 80 mCi in a 10-kg child). As limited antitumorigenic effect is expected at the 10 mCi dose, only 1 patient is planned to receive this dose level if no Grade 3 or higher AEs are observed in the first patient.

The DMC can recommend to stop the trial based on treatment-emergent safety findings (see [Section 4.4.1](#)). In addition, a planned cohort-expansion phase (Part 2) will enable the RP2D to be studied in a larger number of patients.

A maximum of 2 cycles of treatment will be permitted in Part 1, during which the RP2D to be used in Part 2 will be determined based on dose-escalation findings from Part 1, primarily based on the overall safety and tolerability findings across both cycles in Part 1. Once the RP2D has been selected, patients in Part 2 of the trial will be eligible for up to 5 cycles of treatment.

There is no effective salvage treatment for patients with recurrent medulloblastoma, and the prognosis for these patients is poor. With preliminary data suggesting a potential application of omburtamab-based radioimmunotherapy in medulloblastoma patients, an open-label design has been chosen and found to be ethically defendable. Patients with WNT molecular subgroup of medulloblastoma are excluded because Wnt+ recurrent tumors are sensitive to systemic chemotherapy with excellent prognosis.

As medulloblastoma is primarily a disease of childhood, only pediatric or adolescent patients (up to 19 years of age) will be recruited. Patients below the age of 3 years will be excluded because standard-of-care therapy for this age group differs from that for older patients. Patients in both parts must be recurrent or refractory to frontline therapy. In Part 2 only, patients who have recurrent disease must have received second-line chemotherapy for progressive disease. Patients with 2 or more recurrences of medulloblastoma are expected to have short OS times, which may compromise the ability to assess the safety of Lu-DTPA-omburtamab for up to five 5-week cycles in the expansion phase; therefore, such patients will not be eligible for Part 2. Whether the patient has adequate CSF flow for intrathecal therapy will be determined by Ommaya patency/CSF flow assessment as outlined in [Appendix 7](#). Patients with obstructive or symptomatic communicating hydrocephalus are not eligible for Part 1 or Part 2.

### **3.3. Selection of Doses in the Trial**

#### **3.3.1. Selection of DTPA-omburtamab Mass Dose**

All patients dosed in this trial will receive lutetium-177 conjugated to a fixed mass dose of approximately 1 mg DTPA-omburtamab. A mass dose of 1 mg omburtamab has been used and found to be safe in a trial with >170 patients treated with I-omburtamab. It is expected that a specific activity of 100 mCi/mg DTPA-omburtamab will be achievable. The final mass will be determined based on the specific activity of the supplied lutetium-177 (mCi/mg), the age and decay of the isotope, and the efficiency of the labeling process.

The monoclonal antibody in Lu-DTPA-omburtamab is identical to that used in I-omburtamab and the radioimmunotherapy is to be administered via the same route, i.e., an

indwelling device directly into the third or lateral ventricle. Hence, no new toxicities due to the monoclonal antibody or dose route are anticipated.

The nonclinical and clinical data package supporting this trial consists of I-omburtamab nonclinical data and previous human experience, as well as nonclinical safety data using Lu-DTPA-omburtamab and DTPA-conjugated antibody product (DTPA-omburtamab).

DTPA-omburtamab has been tested in a 28-day intracerebroventricular toxicity study in cynomolgus monkeys. DTPA-omburtamab, when administered as a single dose up to 1.5 mg/kg to juvenile cynomolgus monkeys, was well tolerated over the study period. All findings were considered unrelated to the test article and non-adverse. The NOAEL for DTPA-omburtamab in monkey was determined to be 1.5 mg/kg.

At the NOAEL following a single infusion of DTPA-omburtamab to juvenile cynomolgus monkeys, safety margins for a proposed total mass dose of up to 1 mg DTPA-omburtamab are 30-, 60-, and 75-fold in pediatric, adolescent, and adult humans, respectively (for more details, please see the Investigator's Brochure).

### **3.3.2. Selection of Lutetium-177 Dose for Organ Dosimetry**

The dosimetry dose (Day 1 of Cycle 1, in Part 1 only) will be 5 mCi of lutetium-177. This is considered sufficient to deliver quality whole-body planar gamma camera (and SPECT, if possible) scans. If the dosimetry dose of 5 mCi turns out to deliver a too low acquisition of radioactivity count (see [Section 7.2](#)), the dosimetry dose will be increased to 10 mCi for subsequent patients, at the sponsor's discretion.

### **3.3.3. Selection of Lutetium-177 Treatment Dose**

Lutetium-177 and iodine-131 predominantly emit  $\beta$ -radiation with a comparable half-life. From a pure radionuclide perspective, and considering small-volume tumors and minimal residual disease, lutetium-177 is expected to generate two thirds of the same  $\beta$ -ionizing radiation to the tumor compared to iodine-131 ([Table 2](#)). For larger tumors and normal organs, lutetium-177 is conservatively estimated to generate approximately 50% of the decay of iodine-131. The proposed escalation dose levels for Lu-DTPA-omburtamab take into account the energies of the pure radionuclide, the clinical data with I-omburtamab, and preclinical dosimetry estimations for a pediatric patient. Dosimetry calculations from the biodistribution of Lu-DTPA-omburtamab given intrathecally to rats predict lower absorbed doses to all organs except the liver and lower effective doses than I-omburtamab. However, given the myelosuppression observed in our mouse studies, a 10 mCi starting dose level is proposed which corresponds to an 8-fold safety margin over the highest no-adverse-events dose (200  $\mu$ Ci corresponds to 80 mCi in a 10-kg child).

**Table 2: Properties of Lutetium-177 and Iodine-131**

Property	Lutetium-177	Iodine-131
Half-life (days)	6.65	8.03
Main beta energies (average) (keV)	134	97 and 192
Beta dose/decay (MeV/Bq-s)	0.134	0.182
X rays intensity >5% (keV)	None	29-33
Gamma energies (keV)	113; 208	284; 364
Auger cascade total energy (keV)	0.67	0.37
Chemistry	Lanthanide, chelates	Halogen, covalently bound

Clinical safety data of intracerebroventricular administration of I-omburtamab are derived from clinical studies. The monoclonal antibody (omburtamab) used for lutetium-177 labeling is identical to that used for iodine-131 labeling. The radiopharmaceutical is to be administered via the same route (intracerebroventricular administration) via an indwelling device directly into the third or lateral ventricle. Hence, no new toxicities, either due to the monoclonal antibody or to the administration route, are anticipated. A single-center clinical trial at Memorial Sloan Kettering Cancer Center and a multicenter, international clinical trial are ongoing under the governance of Y-mAbs, where more than 200 patients have received the I-labeled omburtamab via intracerebroventricular administration. Most patients had neuroblastoma CNS/leptomeningeal metastases (n = 109); however, 23 patients had the diagnosis refractory/recurrent medulloblastoma. Overall, safety profiles were not markedly different in these patients as compared to the general exposed patient population. In these studies, the doses were reduced by 50% for patients ≤12 months old, and by 33% for patients >12 to <36 months old. However, based on the safety findings in the escalation phase, a flat treatment dose of 50 mCi I-omburtamab was administered to patients aged 3 years and older in the expansion phase. As treatment with I-omburtamab in the 03-133 trial appeared to be safe with manageable acute hematological toxicities, a similar approach will be used in the current trial with Lu-DTPA-omburtamab, which does not include patients under the age of 3 years.

## 4. SELECTION OF TRIAL POPULATION

Prospective approval of protocol deviations to inclusion and exclusion criteria, also known as protocol waivers or exemptions, is not permitted. The World Health Organization 2016 classification are detailed in [Louis et al. 2016](#).

### 4.1. Inclusion Criteria

Patients must satisfy all of the following criteria at the Screening Visit, unless otherwise stated:

1. Histologically confirmed diagnosis of medulloblastoma.
2. SHH, Group 3, or Group 4 according to World Health Organization 2016 classification.
3. Recurrent or refractory to frontline therapy, defined as:
  - a. For Part 1 only: Recurrent (maximum of 2 recurrences) or refractory to frontline therapy. Prior frontline or second-line therapy may involve surgery, craniospinal irradiation, stereotactic radiosurgery, and multi-agent chemotherapy regimens.
  - b. For Part 2 only: Recurrent (maximum of 1 recurrence) or refractory to frontline therapy. Patients with recurrent disease must have received second-line chemotherapy for progressive disease. Prior frontline or second-line therapy may involve surgery, craniospinal irradiation, stereotactic radiosurgery, and multi-agent chemotherapy regimens.
4. Have refractory disease, focal or multifocal recurrent disease, or pure leptomeningeal disease. Cytological or radiographic remission is allowed; however, not simultaneously.
5. Performance status score of 50 to 100, both inclusive, on the Lansky [ $<16$  years] or Karnofsky [ $\geq 16$  years] scales.
6. Aged 3 to 19 years, both inclusive, at the time of the first planned dose of trial treatment.
7. Life expectancy of at least 3 months, as judged by the investigator.
8. Acceptable hematological status prior to first dosing (hematological support is allowed if administered at least 1 week before administration of Lu-DTPA-omburtamab), defined as:
  - a. Hemoglobin  $\geq 8$  g/dL
  - b. White blood cell count  $\geq 1000/\mu\text{L}$
  - c. Absolute neutrophil count  $\geq 1000/\mu\text{L}$
  - d. Platelet count  $\geq 75\ 000/\mu\text{L}$ .

9. Acceptable liver function prior to first dosing, defined as:
  - a. Alanine aminotransferase (ALT) and aspartate aminotransferase (AST)  $\leq 5 \times$  upper limit of normal (ULN)
  - b. Bilirubin  $\leq 1.5 \times$  ULN.
10. Acceptable kidney function prior to first dosing, defined as:
  - a. Estimated glomerular filtration rate (eGFR)  $>60$  mL/min/1.73 m^2, calculated by the 2009 revised Bedside Schwartz Equation ([Appendix 4](#)).
11. Written informed consent from legal guardian(s) and/or child obtained in accordance with local regulations. Pediatric patients must provide assent as required by local regulations.

#### **4.2. Exclusion Criteria**

Patients will be excluded from the trial if they satisfy any of the following criteria at the Screening Visit unless otherwise stated:

1. Obstructive or symptomatic communicating hydrocephalus as determined by Ommaya patency/CSF flow assessment.
2. Any tumor lesion measuring  $>15$  mm in the smallest diameter.
3. Ventriculoperitoneal (VP) shunts without programmable valves. Ventriculo-atrial or ventriculo-pleural shunts.
4. Grade 4 nervous system disorder. Stable neurological deficits due to brain tumor or surgery and hearing loss are allowed.
5. Uncontrolled life-threatening infection.
6. Received radiation therapy (focal or crano-spinal irradiation), systemic or intrathecal cytotoxic chemotherapy, or immunotherapy (including monoclonal antibodies; corticosteroids not included) less than 3 weeks prior to the Dosimetry Dose (or until recovery from clinically significant adverse events). Received nitrosoureas less than 6 weeks prior to the Dosimetry Dose.
7. Received any prior anti-B7-H3 treatment.
8. Non-hematologic organ toxicity Grade 3 or above; specifically, any renal, cardiac, hepatic, pulmonary, and gastrointestinal system toxicity.
9. Other significant disease or condition that in the investigator's opinion would exclude the patient from the trial.

10. Females of childbearing potential (as defined in [Appendix 5](#)) who are pregnant, breast feeding, intend to become pregnant, or are not using highly effective contraceptive methods as defined in [Appendix 5](#) or males who are not using highly effective contraceptive methods as defined in [Appendix 5](#).

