In Part 2, all treatment cycles will consist of a treatment dose on Day 1; the dose level will be the RP2D determined in Part 1. Patients who are not discontinued from treatment will be eligible for up to 5 treatment cycles in Part 2. Dose reductions due to toxicity are permitted in Part 2 only.

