### 3. INVESTIGATION PLAN

#### 3.1. Overall Trial Design and Plan Description

This is a Phase I/II, open-label, safety and efficacy trial in pediatric and adolescent patients (3 to 19 years) with recurrent or refractory medulloblastoma. The trial will be conducted in 2 parts:

- Part 1: a dose-escalation phase with a 3+3 sequential-group design (except for the first dose level, which will consist of a single patient only) of five planned dose levels, and in which up to 25 patients will receive a maximum of two 5-week cycles of treatment with intracerebroventricular Lu-DTPA-omburtamab. Patients will receive a dosimetry dose in Week 1. Treatment doses will follow in Week 2 of the first cycle, and on the first day of Cycle 2. Adjustments to the dosing schedule will be accommodated on a patient-by-patient basis depending on the clinical condition of the patient. A Data Monitoring Committee (DMC) will review the safety data from previous dose levels and provide recommendations on whether dose escalation should continue. The MTD and/or RP2D will be determined.
- Part 2: a cohort-expansion phase in which approximately 24 patients with recurrent or refractory medulloblastoma will receive a maximum of five cycles of treatment with intracerebroventricular Lu-DTPA-omburtamab at the RP2D determined in Part 1.

Patients participating in Part 1 are not permitted to participate in Part 2.

Lu-DTPA-omburtamab will be administered via an indwelling intracerebroventricular access device (e.g., Ommaya reservoir). To avoid an additional procedure and burden to the patient, it can be considered to place the intracerebroventricular access device in connection with any tumor resection procedure that may be performed before entry into the trial. In this case, the informed consent form (ICF) must be signed before the tumor resection.

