### 6.2. Prohibited Concomitant Therapy

The following therapies are prohibited within 3 weeks prior to the first dose and until completion of the EOT Visit:

- Additional cytotoxic anti-cancer therapy.
- Any other IMP.
- Any live viral vaccines.
- Herbal medications with known risk of hepatotoxicity.

The following is prohibited in Part 1 Cycle 1 within 1 week prior to first IMP administration and until 5 weeks after:

- Additional hematological support.

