 Measurements of heart rate, respiratory rate, temperature, and blood pressure. On dosing days, measurements to be taken before and 30 min after the end of the IMP infusion.

 Lansky Scale <16 years, Karnofsky Scale ≥16 years.

 To be performed within 3 weeks prior to first IMP infusion. May be performed on the first dosing day but it must be before IMP administration.

 MRI of the brain and spine will be completed before first IMP administration and at the End-of-Cycle (Day 29) Visit for Cycles 1 and 3 only (±4 days of the actual visit date), EOT Visit (preferably ±4 days of the actual visit date), and each Follow-up Visit (±2 weeks of the actual visit date). MRI can be performed on a different day to the other visit assessments, in accordance with investigational site standards.

 Will be used to evaluate safety and efficacy.

 Beginning 24 hours before Lu-DTPA-omburtamab administration, divided into twice-daily doses for a total of 3 days.

 Given 1-2 hours prior to Lu-DTPA-omburtamab administration, including oral acetaminophen/paracetamol and antihistamine (e.g., diphenhydramine).

 In accordance with [Appendix 1](#) and until the first follow-up visit.

 If CSF cytology sample is positive, it must be repeated within 4 weeks of the positive sampling.

 Cycles 1 and 3 only.

 Drawn and held for culture only if elevated body temperature after dosing suggests infection rather than expected response to ICV dosing. Samples to be taken within 6 hours after completion of Lu-DTPA-omburtamab infusion.

 The ADA samples must be drawn prior to dosing. Serum and CSF samples for ADA analyses will be drawn at baseline, at the start of Cycle 2 (predose), and after last treatment. Presence of ADA will be analyzed at a central laboratory.

 Blood and CSF samples for pharmacokinetics will be drawn in Cycles 1 and 2 only, as per [Table 5](#).

 Pregnancy testing (serum or urine) is mandatory for women of childbearing potential at screening, prior to each dose, and at the EOT Visit.

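### Exclusion criterion 6 counts its washouts back from the dosimetry dose, which Part 2 patients never receive, so read literally Part 2 has no washout for radiation or licensed non-cytotoxic immunotherapy and only half of the one for nitrosoureas

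*Combined protocol and SAP*

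**What the plan says.** Criterion 6 in Section 4.2 excludes patients who had focal or craniospinal radiation, systemic or intrathecal cytotoxic chemotherapy, or immunotherapy "less than 3 weeks prior to the Dosimetry Dose", with an added clause about recovery from clinically significant adverse events. A second sentence sets a longer interval: "Received nitrosoureas less than 6 weeks prior to the Dosimetry Dose". The Synopsis repeats both sentences. Neither place limits the criterion to Part 1 or gives another reference date for Part 2.

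Section 3.3.2 restricts the dosimetry dose to one part: "The dosimetry dose (Day 1 of Cycle 1, in Part 1 only) will be 5 mCi of lutetium-177". The Synopsis describes the other part: "In Part 2, all treatment cycles will consist of a treatment dose on Day 1". The Part 2 schedule (Appendix 3, Table 8) has no dosimetry row. Section 3.1 separates the two populations: "Patients participating in Part 1 are not permitted to participate in Part 2".

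The only other pre-dose window for anti-cancer therapy is in Section 6.2: "The following therapies are prohibited within 3 weeks prior to the first dose and until completion of the EOT Visit". The anti-cancer items listed there are cytotoxic therapy and any other investigational product. Radiation and immunotherapy are not named, and there is no longer interval for nitrosoureas.

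**The concern.** A washout needs a reference date that exists for every patient it governs. Here it does not exist for any Part 2 patient. Section 4 also rules out waivers of the eligibility criteria, so the criterion should be enforceable as it is written.

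The uncovered therapies are not all hypothetical. The Part 2 branch of inclusion criterion 3 states: "Prior frontline or second-line therapy may involve surgery, craniospinal irradiation, stereotactic radiosurgery, and multi-agent chemotherapy regimens". Two things are at stake.

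- **Response.** Table 8, note 9 fixes the timing of the baseline MRI: "To be performed within 3 weeks prior to first IMP infusion". If the 3 weeks before first dose are free of radiation, that MRI always comes after the last radiation. Without the window, radiation could fall between the baseline MRI and the first dose, and later shrinkage could be credited to the trial drug.
- **Safety.** The Part 2 primary endpoint is the number and severity of treatment-emergent events, and Section 8.5.2 counts any event after first administration. Late cytopenia from a nitrosourea would be counted. The blood-count thresholds in inclusion criterion 8 lower this risk, but they apply only at entry.

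**Working it through.** No stated sample size or error rate bears on the point, so the check is mainly a comparison of sections, with some short arithmetic.

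**Step 1. Does the reference date exist in each part?**

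| | Part 1 | Part 2 |
|---|---|---|
| Dosimetry dose given | Yes, Cycle 1 Day 1 (Section 3.3.2) | No (Synopsis; Table 8) |
| Could come from the other part | Not needed | No, crossover is barred (Section 3.1) |
| Criterion 6 can be counted | Yes | No |

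**Step 2. Is the restriction to Part 1 deliberate?** Where eligibility differs by part, the protocol labels it, as in inclusion criterion 3 (branches a and b). Where a rule covers both parts, it uses a neutral reference point: inclusion criteria 6 and 8 to 10 and Section 6.2 all refer to first dosing. Criterion 6 does neither, which points to a drafting slip.

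**Step 3. What does Section 6.2 still cover in Part 2?**

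| Therapy | Intended by criterion 6 | Covered by Section 6.2 | Uncovered in Part 2 |
|---|---|---|---|
| Cytotoxic chemotherapy other than nitrosoureas | 3 weeks | 3 weeks | None |
| Investigational immunotherapy | 3 weeks | 3 weeks (as another investigational product) | None |
| Licensed non-cytotoxic immunotherapy | 3 weeks | Not named | 3 weeks |
| Radiation | 3 weeks | Not named | 3 weeks |
| Nitrosoureas | 6 weeks | 3 weeks (as cytotoxic therapy) | 6 − 3 = 3 weeks |

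The nitrosourea gap runs from about day −42 to day −21. Criterion 6 lists radiation separately from cytotoxic chemotherapy, so it is fair to say that Section 6.2 gives radiation no explicit window.

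**Step 4. Weight of one affected patient.** Section 8.1 plans 24 patients in Part 2, of whom 20 are assumed evaluable for response.

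- Safety: 1/24 = 4.2%.
- Response: 1/20 = 5.0%.

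**Step 5. Illustration for the response rate.** Section 8.1 gives 5 responders in 20 (25%) with a lower 95% limit of 9%. The Clopper-Pearson limits for x responders in n are the Beta quantiles B(0.025; x, n − x + 1) and B(0.975; x + 1, n − x).

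- Plan's figure: x = 5, n = 20 gives 25.0% (8.66% to 49.10%). The lower limit rounds to the stated 9%.
- If one of those five responses was due to prior radiation: x = 4, n = 20 gives 20.0% (5.73% to 43.66%).

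That one response was due to radiation is an assumption. With no affected patients, nothing changes.

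**The case against.** The mismatch in the text is hard to dispute. The strongest case is that little follows from it.

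- **The intent is plain.** Table 7, note 1 treats the dosimetry dose as the first dose in Part 1, Section 6.2 uses the first dose for both parts, and Section 6 sends questions about prior therapy to the Medical Monitor. This stands, and it is why the point is minor.
- **Section 6.1 allows additional anti-cancer treatment after the end-of-treatment visit.** That implies it is not allowed earlier, which fits badly with radiation during screening. The inference is reasonable, but the section deals with concomitant therapy and sets no window before dosing.
- **Criterion 6 has a recovery clause, and exclusions 8 and 9 cover organ toxicity and investigator judgement.** These are real safeguards for Part 2, but none is a washout. The recovery clause is attached to the same missing reference date, and it concerns toxicity, not the response baseline.
- **Treatment-emergent events are counted whatever their cause, and relatedness is summarised separately** (Section 8.5.2). So misattribution has a check. The events would still enter the primary endpoint's count.
- **The effect on response is a chain of assumptions.** Nothing in the documents shows that radiation, nitrosoureas or licensed immunotherapy are likely just before Part 2 entry. Radiation given slightly more than 3 weeks before dosing could also cause later shrinkage, so a correct reference date would not remove that bias entirely. Both points stand, and the response figures should be read only as an illustration.

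**Conclusion.** The concern holds as a minor inconsistency, with high confidence in the wording error. As written, criterion 6 sets no countable washout for Part 2. After Section 6.2 is credited, three gaps remain: radiation, licensed non-cytotoxic immunotherapy, and nitrosoureas in the earlier 3 of their 6 weeks.

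The practical effect is limited to any Part 2 patient enrolled inside an intended washout because a site read the text literally. The documents give no basis for estimating how many, and the answer may be none. The shift in response rate from 25% to 20% depends on one such patient being enrolled and responding because of earlier radiation. The 3-week and 6-week intervals themselves are not in question, and no sample size or error rate is affected.

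**What to change.** In criterion 6 of Section 4.2 and in the matching Synopsis criterion, replace the dosimetry dose with: *the first dose of IMP (dosimetry dose in Part 1, first treatment dose in Part 2)*. Keep the 3-week and 6-week intervals.

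This takes four replacements of one phrase, two in each place. Part 1 is unchanged. Part 2 gains the intended 21 days for radiation, cytotoxic chemotherapy and immunotherapy, and 42 days for nitrosoureas. Sample size and procedures do not change.
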